Clinical Trials Unit	
Pragmatic Clinical Trials Unit (PCTU) Centre for Primary Care and Public Health Blizard Institute [name] [contact]

Key Protocol Contributors	
[name] [name] [name] Unit for Social and Community Psychiatry Newham Centre for Mental Health

	
[name] [contact] Emails: [contact]; [contact]; [contact]

Statistician	
[name] Pragmatic Clinical Trials Unit (PCTU) Centre for Primary Care and Public Health Blizard Institute [name] [contact] Email: [contact]

Committees	
Programme Management Group (co-applicants), Lived Experience Advisory Group

STUDY SUMMARY

Study Title	Assessing social contacts and social activities of people with psychosis
Internal ref. no. (or short title)	SCENE (WP1)
Study Design	Mixed methods cross-sectional survey
Study Participants	Patients with a diagnosis of a psychosis-related condition (ICD10 F20-29); aged 18-65; receiving care from outpatient secondary mental health services or in primary care; capacity to provide informed consent; ability to communicate in English
Planned Sample Size	500 patients
Study duration	Month 1-13
Planned Study Period	1 st of June 2017-30 th of June 2018
Study aims and objectives	
Aim: To assess social contacts, activities and wishes to expand social networks of people with psychosis
 
Objectives:
 
 1. Assessing wishes of people with psychosis for expanding their social networks in order to estimate recruitment rates for a future clinical trial. 2. Assessing social contacts and social activities of people with psychosis 3. Identifying patient-level characteristics associated with social contacts and social activities

FUNDING AND SUPPORT IN KIND

FUNDER(S) (Names and contact details of ALL organisations providing funding and/or support in kind for this trial)	FINANCIAL AND NON FINANCIAL SUPPORT GIVEN
National Institute for Health Research	Programme Grant for Applied Research
East London NHS Foundation Trust (supported by Noclor)	Study sponsorship
East London NHS Foundation Trust	NHS support costs. Permission to conduct study on Trust premises with Trust employees and service users
Tees, Esk & Wear Valleys NHS Foundation Trust	NHS support costs. Permission to conduct study on Trust premises with Trust employees and service users

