7 STATISTICS AND DATA ANALYSIS

The analysis of the data will be discussed with the LEAP, which will have been established at the start of the programme and the LEAP members will help interpretation of the findings.

The number of screened participants, eligible participants and of those who refused participation or were not approached, and reasons for this where available will be recorded. The number and percentages of people who are willing and are not willing to participate in a future trial and of the reasons for this will be calculated. The distribution of the number of contacts in the sample and of the number of social activities reported by participants and the number of those willing to participate in a trial will be presented using descriptive statistics, including mean, median and standard deviation.

We wish to explore which socio-demographic (including social deprivation metrics and urbanicity) and clinical characteristics are associated with the number of social contacts and social activities, in order to identify patient characteristics (and potentially subgroups) which are associated with social isolation. Social deprivation and urbanicity metrics for each participant will be calculated from their LSOA codes bases on the data provided by the Office for National Statistics (English indices of deprivation 2015, Census 2011). We will examine the distributions of all sociodemographic and clinical characteristics and their correlation with each other. For any variables that are highly correlated with each other we will discuss and decide which variables to include in our modelling. We will exclude any binary variables where the prevalence is extreme and any variables with large numbers of missing values since these will not be useful in prediction. We will assess the presence of univariate associations between all remaining socio-demographic and clinical variables (including BPRS scores) and number of social contacts or social activities. Any variables that have a statistically significant relationship with social contacts or social activities univariately at the 10% level will be included in a multivariate model.

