7.2 Sample size calculation

Patients will be randomly selected for approach by clinicians or CSOs. The overall sample size will be 500 patients, which will give us a sufficiently robust estimate of later recruitment rates. If the rate of patients meeting the inclusion criteria and expressing a willingness to participate in a trial was 50%, we would estimate that with a confidence interval of 40% to 60%, i.e. with a margin of error of 10% which is sufficient for the given purpose.

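### Letting a univariate p < 0.10 test decide entry to the multivariable model can lose masked characteristics, deprivation and urbanicity included, and distorts estimates for variables that only just pass

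*Protocol*

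**What the plan says.** The Study Summary gives Objective 3 as "Identifying patient-level characteristics associated with social contacts and social activities". Section 7 introduces the analysis with "We wish to explore which socio-demographic (including social deprivation metrics and urbanicity) and clinical characteristics are associated" with the two outcomes, and gives its purpose as "in order to identify patient characteristics (and potentially subgroups) which are associated with social isolation".

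The steps in section 7 run in this order:

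1. Inspect the distributions and mutual correlations of the characteristics.
2. Choose among highly correlated variables by discussion.
3. Remove binary variables of extreme prevalence and variables with much missing data.
4. Test every remaining variable singly against contacts or activities.
5. Enter those with a "statistically significant relationship with social contacts or social activities univariately at the 10% level will be included in a multivariate model".

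The section names no variable that stays whatever its p-value, and no allowance for the selection. Section 2 (Rationale) says it is not known how neighbourhood deprivation and inequality relate to isolation in this population. Amendment S1 in Appendix 2 added the collection and use of postcodes and LSOA codes.

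**The concern.** Step 5 is a fixed commitment in the protocol, not a detail left open for an SAP. The test that admits a variable is unadjusted, while the question in Objective 3 is better answered by an adjusted association. The two differ when candidates are correlated, and the protocol itself expects correlated candidates.

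Two things can go wrong. First, a characteristic with a real adjusted association can look flat on its own and be discarded. Those that remain are then not adjusted for it. Deprivation and urbanicity could leave the adjusted analysis this way on one unadjusted test, although the study collects postcodes in order to examine them. Second, a variable admitted because its p-value was small in these data is then estimated from the same data as if it had been chosen in advance.

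**Working it through.** **Inputs.** From the protocol: 500 patients (section 7.2) and the 10% entry level (section 7). Section 7.2 sizes the study on one proportion, so there is no planned figure for the regression to reproduce. Effect sizes, correlations and overdispersion are not in the protocol and are assumed here.

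Count simulations: 500 patients, two standardised predictors, mean count 1.5, negative-binomial overdispersion with shape 0.7 unless stated, quasi-Poisson fits, 5% test in the final model. Linear simulations: 500 patients, residual SD 1, 2,000 replicates, 20 candidates.

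**1. Masking.** For standardised, jointly normal predictors with adjusted effects b1 and b2 and correlation r, the univariate effect of the first is b1 + r × b2. Power below is for the first predictor.

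| Effects (log rate per SD) | r | Univariate effect | Power, both fitted | Power, screened first |
|---|---|---|---|---|
| +0.20 / -0.20 | 0.3 | 0.20 - 0.06 = 0.14 | about 83% | about 62% |
| +0.20 / -0.20 | 0.5 | 0.20 - 0.10 = 0.10 | about 75% | about 37% |
| +0.20 / -0.20 | 0.6 | 0.20 - 0.12 = 0.08 | about 68% | about 25% |
| +0.20 / +0.20 | 0.5 | 0.20 + 0.10 = 0.30 | about 73% | about 73% |

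With milder overdispersion the loss in the opposing case at r = 0.5 remains: about 85% against 47% at shape 1, and 92% against 57% at shape 1.5. In the same-direction case at shape 1, both predictors passed the screen in over 99% of runs, and power was 83.5% either way.

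**2. The lost confounder** (linear model, r = 0.5). With effects +0.40 and -0.20, the second variable's univariate effect is -0.20 + 0.5 × 0.40 = 0, so the screen removes it in about 90% of samples. The first variable then estimates 0.40 + 0.5 × (-0.20) = 0.30. The simulated mean when selected is 0.306, with 42.6% coverage of the 95% CI; the full model gives 0.400 with about 95%. With +0.20 and -0.10 the expected value is 0.15. The simulation gives 0.159 with 86.7% coverage.

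**3. Selection.**
- *Independent null variable.* P(p < 0.05 given p < 0.10) = 0.05/0.10 = 0.50, so 95% CI coverage given entry is about 50%. With 20 null candidates, 10.0% passed. Of those, 50.3% had p < 0.05 in the final model, and coverage was 49.7%. The full model gave 5.1% and 94.9%.
- *Overall false positives.* 0.10 × 0.50 = 0.05, the nominal level. Count simulations gave the same rate by both routes (5.4% and 5.4% in one run, about 7% and 7% in another).
- *Weak true effect.* A log-rate effect of 0.12 averages about 0.167 when selected, a factor of 0.167/0.12 = 1.39 (rate ratio 1.18 instead of 1.13). The inflation is smaller when overdispersion is milder. In the linear model an effect of 0.07 is selected 46% of the time and then averages 0.106; the full model gives 0.070. Coverage given selection stayed at 94.9% there, so for weak true effects it is the point estimate that suffers.

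**4. Room for a full model.** 500/20 = 25 patients per parameter; 500/30 = 16.7; 500/50 = 10. The protocol does not state the number of candidates.

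**The case against.** The strongest reply is that the harm is conditional and the stakes are modest. Masking needs opposing effects, and nothing in the protocol shows that deprivation, urbanicity, diagnosis and symptoms behave that way. Where effects run in the same direction, screening costs no power. The 50% coverage follows almost by definition from conditioning on a small p-value, and the overall count of false-positive characteristics is unchanged. The analysis is described as exploratory. All of this stands, and it limits the point to what the rule can do.

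Exploratory status does not rescue the rule itself. It excuses the absence of multiplicity control, but it does not make a discarded confounder reappear or undo selection inflation, and the product of the analysis is a list of characteristics.

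A reader might infer more than the protocol supports:

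- *That a null variable has a 19% chance of entry because of the word "or".* 1 - 0.9² = 0.19 requires independent outcomes and one shared list of predictors. Screening each outcome separately is an equally natural reading and gives 10%. Entry of a null variable is in any case no harm by itself, since a full model includes it too.
- *That collinear variables are chosen by looking at the outcomes.* The text says "For any variables that are highly correlated with each other we will discuss and decide which variables to include in our modelling", and it places this before the outcome tests.
- *That dropping variables with much missing data is a further fault.* That is common practice in exploratory work, and the reference to prediction there is a matter of one word.

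**Conclusion.** The point holds in a limited form. The protocol fixes a weaker selection rule than it needs for Objective 3. Under assumed opposing effects of 0.20 per SD at correlation 0.5, the rule halves the power to find a real characteristic (about 75% to about 37%). Where the masked variable is a confounder, it biases the estimate that is kept. Under same-direction effects it costs nothing in power. Weak effects that pass are overstated, and intervals for null variables that pass cannot be taken at face value.

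These sizes rest on the assumed effects, correlations and overdispersion. They show what is possible, not what will be found. The protocol does not support a claim that screening will drop confounded variables in general, that it raises the false-positive rate, or that 500 patients will carry any full model, because the candidate list is not given. The recruitment-rate estimate, for which the protocol says "The overall sample size will be 500 patients, which will give us a sufficiently robust estimate of later recruitment rates", is not touched.

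**What to change.** Replace the p < 0.10 entry rule in section 7 with the following:

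- List the candidate predictors on subject-matter grounds before the outcomes are examined. Always include deprivation, urbanicity and the main demographic and clinical variables.
- Settle collinear pairs without reference to the outcomes, as the stated order already allows, and say so explicitly.
- Fit all listed predictors in one count model per outcome (for example negative binomial), and report every adjusted estimate with its 95% CI, not only the significant ones.
- Keep the univariate results as description only.
- State the number of parameters. About 20 gives 25 patients each; if the list is too long for 500 patients, use a penalised model.

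The cost is a change of wording, a little more analysis, and slightly wider intervals from keeping variables that turn out to be null. No further patients or data are needed.

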7.1 Qualitative Data Analysis Plan

Responses to open questions will be analysed using content analysis to identify trends and patterns in the data by categorising words that share the same meaning (Hsieh and Shannon, 2005; Vaismoradi, Turunen and Bondas, 2013; Cavanagh, 1997). Qualitative content analysis will be conducted on participants' responses to open questions that form part of the survey. An inductive approach will be used to provide new insights and richer understanding of the data without using preconceived

SCENE work package 1 Protocol V4.0 27/11/2017

IRAS ID: 228169

categories (Hsieh and Shannon, 2005; Vaismoradi, Turunen and Bondas, 2013). Inductive content analysis will be conducted following steps as outlined by Elo and Kyngäs (2007). Three members of the research team will familiarise themselves with the steps of analysis and then independently analyse the data using open coding (making notes and headings in the text to describe the content). Similar codes will then be grouped under themes, and the identified themes and subthemes will then be checked and refined. This method will aid conformability and allow the resulting themes to accurately represent the voice of participants rather than researchers (Elo et al., 2007).

The analysis will inform the final decision regarding whether primary care services are included in addition to secondary care services within the next phase of the project (not included within this application).

The findings will have a direct impact on all further information material and dissemination.

7.2 Sample size calculation

Patients will be randomly selected for approach by clinicians or CSOs. The overall sample size will be 500 patients, which will give us a sufficiently robust estimate of later recruitment rates. If the rate of patients meeting the inclusion criteria and expressing a willingness to participate in a trial was 50%, we would estimate that with a confidence interval of 40% to 60%, i.e. with a margin of error of 10% which is sufficient for the given purpose.

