12.2 Appendix 2 – Amendment History

Amendment No.	Protocol version no.	Date issued	Author(s) of changes	Details of changes made
2	2	10/08/17	[name]	
 • Key Study Contacts, page 4: information on trial co-ordinator has been added; • Study Summary, page 6; and section 7.2: planned sample size increased. • Section 4. Study Setting, page 15: has been changed to reflect the possibility of including more sites in addition to the 3 core ones.
3	3	22/08/17	[name]	
 • Study Summary, page 6; and section 7.2: planned sample size increased.
S1	4		[name]	
 • Study Summary, page 6; and section 7.2, p19: planned sample size increased to 500. • Study Procedures, Survey, page 16: added 'or primary care setting, quiet rooms in the University where researchers are employed' • Study Summary, page 6; Study setting and Inclusion Criteria p 15; 6.1.1 Patient Identification, p15: added option to recruit from the primary care teams. • 1. Rationale, page 12; 6. Study procedures, p.16 7. Statistics and data analysis, p.18., References p.24-25. Added explanations on why and how we will collect and use postcodes and LSOA codes.

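### The 10-point margin of error in section 7.2 does not follow from 500 patients: at 95% it is about 4.4 points before any clustering, and 10 points needs only about 97 patients

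*Protocol*

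**What the plan says.** Protocol section 7.2 fixes the sample and gives its reason in one sentence: "The overall sample size will be 500 patients, which will give us a sufficiently robust estimate of later recruitment rates". The Study Summary gives the same planned number.

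The precision statement follows. It takes a 50% rate of patients who meet the inclusion criteria and are willing to take part in a trial, and concludes: "we would estimate that with a confidence interval of 40% to 60%, i.e. with a margin of error of 10% which is sufficient".

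On sampling, 7.2 says only: "Patients will be randomly selected for approach by clinicians or CSOs". It gives no confidence level, design effect, intracluster correlation (ICC) or allowance for non-response, and no smaller denominator to which the interval would apply. The number is described as an overall one, not one per site or care setting.

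**The concern.** Estimating recruitment rates for a future trial is part of objective 1 in the Study Summary. Section 7.2 is the only place where the protocol links the sample size to a precision for that objective. The interval quoted there is recognisably the one that goes with a sample of about 100, not 500.

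If so, the sample-size statement does not do its job. A reader who accepts 10 points as enough finds a calculation that supports about 97 patients and a plan to interview 500. A reader who accepts 500 is told to expect a wider interval than simple random sampling would give. Either way, an ethics or funding reviewer cannot see from 7.2 why the number is 500.

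**Working it through.** **Inputs, all from section 7.2 unless noted**

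- n = 500, overall
- p = 0.50
- stated interval 40% to 60%, so half-width d = 0.10
- confidence level: not stated; two-sided 95% assumed (z = 1.96), other levels tried below
- design effect: not stated; 1 taken first

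**1. Trying to reproduce the stated margin**

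Half-width = z × √(p(1 − p)/n) = 1.96 × √(0.25/500) = 1.96 × 0.02236 = 0.0438.

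The interval is 45.6% to 54.4%. The stated 10 points is not reproduced. Ratio of margins: 10/4.38 = 2.28.

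**2. Does the interval method matter?** At n = 500 and 95%:

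| Method | Half-width (points) |
|---|---|
| Wald | 4.38 |
| Wald, continuity-corrected | 4.48 |
| Wilson | 4.37 |
| Clopper-Pearson | 4.47 |

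No.

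**3. Does the confidence level matter?** Wald, n = 500:

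| Level | Half-width (points) |
|---|---|
| 90% | 3.7 |
| 95% | 4.4 |
| 99% | 5.8 |
| 99.9% | 7.4 |

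Ten points would need z = 0.10/0.02236 = 4.47, a level of about 99.999%. No conventional level closes the gap.

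**4. Sample size that matches 10 points**

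n = z² × p(1 − p)/d² = 1.96² × 0.25/0.01 = 96.04, so 97. By the other methods it is about 93 (Wilson), 104 (Clopper-Pearson) or 106 (continuity-corrected). Ratio of sample sizes: 500/96.04 = 5.2. This is the square of the ratio of margins (2.28² = 5.2), so 2.3 and 5.2 describe the same discrepancy on two scales.

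**5. Design effect that would rescue the figure**

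The design effect needed for 10 points at n = 500 is 5.2. With design effect = 1 + (m − 1) × ICC for m patients per cluster, this would take an ICC of about 0.22 with 20 per cluster, or about 0.025 with 167 per cluster.

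The protocol gives neither an ICC nor a number of clusters. As an assumed range, take ICC 0.01 to 0.05 and 6 to 20 equal clusters:

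- ICC 0.01, 20 clusters (m = 25): design effect 1 + 24 × 0.01 = 1.24; half-width 4.38 × √1.24 = 4.9 points
- ICC 0.05, 6 clusters (m = 83.3): design effect 1 + 82.3 × 0.05 = 5.12; half-width 4.38 × √5.12 = 9.9 points

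**6. Per-site precision**

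Three equal sites (about 167 each) would give 7.6 points per site, and five equal sites (100 each) 9.8 points. The second is close to the stated figure, but 7.2 describes an overall sample and sets no per-site aim.

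**The case against.** The strongest defence is clustering. Sections 4 and 6.1.1 describe recruitment from several Trusts and from team caseloads, so some clustering is to be expected, and the upper end of the assumed range in step 5 (9.9 points) almost reaches the stated margin. This stands in part: 4.4 points is the simple-random-sampling figure, and the documents do not support reading it as the margin the survey will achieve. It does not rescue 7.2, because an allowance of that size would be the input that drives the calculation, and it is not mentioned.

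The second defence is that the error is on the safe side. That is right. Under simple random sampling, and across the assumed clustering range, 500 patients meet the 10 points that the protocol asks for. Only outside that range would they miss it: three clusters of 167 with an ICC of 0.05 give a design effect of 9.3 and 13.4 points, and section 4 provides for Trusts beyond the first three.

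Two stronger readings are tempting and should be resisted:

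- A reader might infer that 500 is five times more than the study needs. The documents do not show that. Objectives 2 and 3, and the modelling in section 7, also use the sample. Section 7.2 simply does not cite them as reasons for the number.
- A reader might infer that an old margin was left in place when the sample grew. The amendment history records increases in section 7.2 in versions 2, 3 and 4, the last as "planned sample size increased to 500". It gives neither the earlier numbers nor the earlier margin, so this is conjecture, and the point does not depend on it.

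It is also fair to say that a later trial would be planned from the observed willingness rate and its own interval, not from this planning sentence. That limits the practical harm.

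**Conclusion.** Wrong as written; moderate severity. The 40% to 60% interval does not belong to 500 patients at a 50% rate. The margin is about 4.4 points (45.6% to 54.4%), so the stated one is about 2.3 times too wide, and about 97 patients would deliver it. This rests on a two-sided 95% level and simple random sampling. The conclusion is insensitive to the interval method and to any conventional confidence level. It would change only with a design effect near 5.2, or a subgroup of about 97 as the real target, and the protocol states neither.

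What fails is the justification, not the survey. The sample is not too small for objective 1, and the misstatement alters no planned analysis. It matters because it is the sole quantitative argument for the number of patients to be interviewed.

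**What to change.** In section 7.2, do one of the following:

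- State the confidence level and replace the interval. For example: *with 500 interviewed patients, a willingness rate of 50% would be estimated with a 95% confidence interval of about 45.6% to 54.4% (margin 4.4 points), before any allowance for clustering.*
- If the 10-point margin is intended, state what it rests on. This is either the assumed design effect (about 5.2, with the ICC and cluster size behind it) or the subgroup, such as a Trust or care setting, in which 10 points is wanted, with the roughly 97 patients per subgroup that this requires.

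The cost is one or two sentences. Enrolment, procedures and analysis are unchanged.
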